ECOG	Eastern Cooperative Oncology Group
EDC	Electronic data capture
Electronic Source Data (eSource)	source data captured initially into a permanent electronic record used for the reconstruction and evaluation of a trial.
End of Study for Individual Subject	Excluding early termination of the study, the EOS visit for individual subjects will be defined as up to 2 weeks after the last subject in the trial completes their LTFU visit 1 year after the last dose of investigational product.
End of Study (EOS, primary completion)	defined as the date when the last subject is assessed or receives an intervention for the final collection of data for the primary endpoint(s).
End of Study (end of trial)	defined as the date when the last subject across all sites is assessed or receives an intervention for evaluation in the study (ie, last subject last visit), following any additional parts in the study (eg, long-term follow-up), as applicable
End of Treatment Period (EOTP)	defined as the latest assessment date of the follow-up visit (7 days [\pm 1 day] after the last dose of investigational product). If a subject does not complete an follow-up visit, then EOTP will be 7 days after the last dose of investigational product or the EOS date, whichever is earlier

FOLFOX	Oxaliplatin, 5-FU, leucovorin
GSO-DM	Global Study Operations-Data Management
██████████	██████████
IBG	Independent Biostatistics Group
ICH	International Council for Harmonisation
IP	Investigational product
LTFU	Long-term follow-up
MDS	Myelodysplastic syndrome
MedDRA	Medical Dictionary for Regulatory Activities
SAP	Statistical analysis plan
SMQ	Standardized MedDRA query
Source Data	Information from an original record or certified copy of the original record containing patient information for use in clinical research. The information may include, but is not limited to, clinical findings, observations, or other activities in a clinical trial necessary for the reconstruction and evaluation of the trial. Source data are contained in source documents (original records or certified copies). (ICH Guideline [E6]). Examples of source data include Subject identification, Randomization identification, and Stratification Value.
SSAP	Supplemental statistical analysis plan
TPO	Thrombopoietin
ULN	Upper limit of normal

1. Introduction

The purpose of this Statistical Analysis Plan (SAP) is to provide details of the statistical analyses that have been outlined within the protocol for study 20140346, Romiplostim dated **7/29/2021**. The scope of this plan includes the **interim analysis**, the primary analysis and the final analysis will be executed by the Amgen Global Biostatistical Science department unless otherwise specified

[REDACTED]. Pharmacokinetics (PK) analyses will be provided by

Department of Clinical Pharmacology and Modeling and Simulation.

[figure not shown]
2. Objectives, Endpoints and Hypotheses

2.1 Objectives and Endpoints

Objectives	Endpoints
Primary	

 to evaluate the efficacy of romiplostim for the treatment of chemotherapy-induced thrombocytopenia (CIT) in patients receiving chemotherapy for the treatment of gastrointestinal, pancreatic, or colorectal cancer, measured by the ability to administer on-time, full-dose chemotherapy 	
 no thrombocytopenia-induced modification of any myelosuppressive treatment agent in the second and third cycles of the planned on-study chemotherapy regimen. Thrombocytopenia-induced modifications include chemotherapy dose reduction, delay, omission, or chemotherapy treatment discontinuation due to platelet counts below $100 \times 10^9/L$
Secondary	

 to compare the treatment effect of romiplostim with that of placebo on the depth of platelet nadir 	
 the depth of the platelet count nadir from the start of the first on-study chemotherapy cycle through the end of the treatment period

 to compare the treatment effect of romiplostim with that of placebo on the time to first platelet response 	
 the time to first platelet response, defined by platelet count $\geq 100 \times 10^9/L$ in the absence of platelet transfusions during the preceding 7 days

 to compare the treatment effect of romiplostim with that of placebo on the incidence of \geq grade 2 bleeding events 	
 the duration-adjusted event rate of \geq grade 2 bleeding events, as assessed by Common Terminology Criteria for Adverse Events (CTCAE) version 5.0 grading scale

• to compare the treatment effect of romiplostim with that of placebo on overall survival	
• overall survival

• to compare the treatment effect of romiplostim with that of placebo on the incidence of platelet transfusions	
• platelet transfusion(s) during the treatment period

• to compare the treatment effect of romiplostim with that of placebo on the proportion of patients achieving platelet response	
• achieving a platelet count $\geq 100 \times 10^9/L$ at any time after study day 1 to week 4 (ie, 7 days after the planned third dose of investigational product) and in the absence of platelet transfusions during the preceding 7 days

• overall safety of romiplostim	
• adverse events, including treatment-emergent adverse events, fatal adverse events, serious adverse events, and clinically significant changes in laboratory values.• anti-romiplostim antibodies and antibodies to thrombopoietin (TPO)• myelodysplastic syndromes and secondary malignancies

Exploratory

2.2 Hypotheses and/or Estimations

It is anticipated that romiplostim will raise platelet counts faster than placebo, resulting in more on-time and full-dose delivery of chemotherapy cycles in subjects with CIT and decreasing the incidence of platelet transfusions and bleeding events.

3. Study Overview

3.1 Study Design

This is a phase 3, randomized, placebo-controlled, multicenter, international study for the treatment of CIT in adult subjects receiving **oxaliplatin**-based chemotherapy for the treatment of gastrointestinal, **pancreatic**, or colorectal cancer. Subjects must have a platelet count $\leq 85 \times 10^9/L$ on day 1 of the study. The study will consist of a screening period of up to 4 weeks, a treatment period long enough to allow for assessment of 3 planned cycles of chemotherapy, a follow-up visit, and long-term follow-up (LTFU). Given that subjects will be assessed for 3 planned cycles of chemotherapy, the **oxaliplatin**-based chemotherapy cycles are 2-3 weeks in duration, and the investigational product dose adjustment guidelines allow for up to 12 weeks of dosing before a subject is declared a non-responder, the majority of study subjects will receive investigational product (IP) for a range of between 7-21 weeks.

Once eligibility is confirmed, subjects will be randomized on day 1 of the study in a 2 to 1 ratio to receive either romiplostim or placebo, respectively. Randomization will be stratified by tumor type and by baseline platelet count ($< 50 \times 10^9/L$, $\geq 50 \times 10^9/L$). Baseline platelet count is defined as last platelet count measured prior to the time of the planned investigational product administration. Gastrointestinal cancers, including tumors of the esophagus or stomach, will be included in one stratum, **pancreatic cancers in a second stratum, and colorectal cancers, including adenocarcinomas of the colon or rectum, will be included in a third stratum**. Subjects will then enter the treatment period, during which time they will return to the clinic weekly for local platelet counts, undergo dose titrations as needed, and investigational product administration. If there are multiple platelet values performed on a study visit date, the platelet value from the test performed most immediately prior to the time of the planned investigational product and/or non-investigational product administration will be recorded as the platelet value for that study visit date and will be used to determine the subject's dose of investigational product and, when applicable, chemotherapy dose modifications which include dose reductions, delays, omissions, and discontinuations. Subjects will receive weekly subcutaneous injections of investigational product throughout the treatment period, starting at 2 $\mu g/kg$ and increasing by

increments of 1 μ g/kg to a maximum dose of 10 μ g/kg to reach a target platelet count of $\geq 100 \times 10^9/L$. **Dose adjustment rules will be followed according to protocol Table 7-1. If the subject will be receiving concomitant chemotherapy on a study visit date, investigational product will be administered immediately after the completion of chemotherapy infusion on chemotherapy day 1. If continuous infusion 5 fluorouracil (5-FU) over 46-48 hours is part of the chemotherapy regimen the investigational product may be administered prior to beginning or during the continuous infusion 5-FU.**

Subjects will have a follow-up visit 1 week after the last dose of investigational product.

Subjects will have their first in-clinic LTFU visit 30 (+ 5) days after the last dose of investigational product (Safety Follow-up 1). Subjects will be contacted 30 (+5 days) after the last dose of the last on-study cycle of chemotherapy (up to 3 cycles) to collect adverse event information except for females who are in addition required to come to clinic for a highly sensitive urine **or serum** pregnancy test (Safety Follow-up 2). Subjects will remain in LTFU until the last subject in the trial completes the LTFU visit 1 year after the last dose of investigational product. During the LTFU period, all subjects will be followed by phone or in clinic every 12 weeks (\pm 2 weeks) **from the last dose of investigational product** until the end of study (EOS) visit. All subjects should complete EOS visit up to 2 weeks after the last subject in the trial completes their LTFU visit 1 year after the last dose of investigational product.

During LTFU subjects will be followed for the diagnosis of, or progression to, secondary malignancies (including myeloid malignancies) or myelodysplastic syndromes, as well as vital status and cause(s) of death.

[figure not shown]
3.2 Sample Size

A sample size of 162 is chosen with 2:1 randomization ratio (108 romiplostim, 54 placebo), stratified by tumor type (**Gastrointestinal, Pancreatic, and Colorectal**) and baseline platelet count ($< 50 \times 10^9/L$, $\geq 50 \times 10^9/L$). In two small studies ([Al Samkari et al, 2018](#); [Soff et al, 2017](#)), few patients with CIT spontaneously recovered their platelet counts to adequate levels: 5 of 22 (23%) and 1 of 8 (13%), respectively. A phase 2 study showed 75% (24 out 32 subjects) subjects resumed chemotherapy after treatment with romiplostim ([Soff et al, 2017](#)). From retrospective reviews, between 65% (13 of 20 subjects) and 82% (18 of 22 subjects) subjects did not have any thrombocytopenia-induced chemotherapy dose modifications after treatment with romiplostim ([Parameswaran et al, 2014](#); [Al-Samkari et al, 2018](#)).

Thrombocytopenia-induced chemotherapy dose modifications in one cycle may be correlated with the previous cycle outcome. Assume that p is the probability of receiving a planned on-study chemotherapy regimen with no thrombocytopenia-induced chemotherapy dose modifications in a cycle, ρ is the cycle correlation and the correlation is the same in romiplostim group and control group, the probability of receiving the planned chemotherapy regimen with no thrombocytopenia-induced chemotherapy dose modifications in two subsequent cycles, $p_{2,3}$ for Cycle 2 and 3, can be calculated as $p_{2,3} = p^2 + \rho p(1 - p)$.

A higher cycle correlation is shown to be associated with a lower odds ratio of treatment effect for romiplostim vs control ([Figure 3-1](#)).

Figure 3-1. Relationship Between Cycle Correlation and Treatment Effect^a

^a Assume 30% and 60% probability of having no dose modifications in one cycle for placebo and romiplostim respectively.

From conservative considerations, probability of receiving the planned on-study chemotherapy regimen with no thrombocytopenia-induced chemotherapy dose modifications in one cycle for subjects treated in placebo group and romiplostim group is assumed to be 30% and 60% respectively, with a strong cycle correlation of 0.7 between two subsequent cycles. The odds ratio of having no thrombocytopenia-induced chemotherapy dose modifications in two cycles for romiplostim vs placebo is 3.6 ([Figure 3-1](#)).

The chosen sample size of 162 (108 romiplostim, 54 placebo) will provide 93% power to detect the treatment effect between the romiplostim group and the placebo group as defined in the

primary endpoint at a two-sided significance level of 0.05 using a Cochran-Mantel-Haenszel (CMH) test. Power calculations were performed in East version 6.4 using a 2-sided CMH test at significance level of 0.05 and stratification by tumor type and baseline platelet count ($< 50 \times 10^9/L$, $\geq 50 \times 10^9/L$).

One interim analysis will be performed at approximately 81 subjects (50% of the planned sample size) completing three cycles of chemotherapy. The non-binding futility boundary is constructed using Lan-DeMets spending function with the O'Brien-Fleming approach. Assuming an observed 35% of subjects in the control arm with no thrombocytopenia-induced chemotherapy dose modification in one cycle, the power is estimated to be 84% at the interim analysis and the probability of stopping for futility is 2%.

4. Covariates and Subgroups

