**Figure 10-1. Relationship Between Cycle Correlation and Treatment Effecta**

a Assume 30% and 60% probability of having no dose modifications in one cycle for placebo and romiplostim respectively.

From conservative considerations, probability of receiving the planned on-study chemotherapy regimen with no thrombocytopenia-induced chemotherapy dose modifications in one cycle for subjects treated in placebo group and romiplostim group is assumed to be 30% and 60% respectively, with a strong cycle correlation of 0.7 between two subsequent cycles. The odds ratio of having no thrombocytopenia-induced chemotherapy dose modifications in two cycles for romiplostim vs placebo is 3.6 (Figure 10-1).

The chosen sample size of 162 (108 romiplostim, 54 placebo) will provide 93% power to detect the treatment effect between the romiplostim group and the placebo group as defined in the primary endpoint at a two-sided significance level of 0.05 using a Cochran-Mantel-Haenszel (CMH) test. Power calculations were performed in East version 6.4 using a 2-sided CMH test at significance level of 0.05 and stratification by tumor type and baseline platelet count ( $< 50 \times 10^9/L$ ,  $\geq 50 \times 10^9/L$ ).

**One interim analysis will be performed at approximately 81 subjects (50% of the planned sample size) completing three cycles of chemotherapy. The non-binding futility boundary is constructed using Lan-DeMets spending function with the O'Brien-Fleming approach. Assuming an observed 35% of subjects in the control arm with no thrombocytopenia-induced chemotherapy dose modification in one**

cycle, the power is estimated to be 84% at the interim analysis and the probability of stopping for futility is 2%.

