#### **10.3.1 Planned Analyses**

##### **10.3.1.1 Interim Analysis and Early Stopping Guidelines**

**One interim futility analysis will be performed at approximately 81 subjects completing three cycles of chemotherapy. The primary endpoint, which is the proportion of subjects with no thrombocytopenia-induced chemotherapy dose modification in the second and third cycles of the planned on-study chemotherapy regimen, will be analyzed at the interim analysis. Dose modification assessments will be based on the central review by the independent adjudication committee. The futility boundary for the primary endpoint is p-value of 0.438, which corresponds to an OR of 1.086. The study may be stopped for futility if the non-binding futility boundary is crossed.**

**Due to slow enrollment, there will be no enrollment pause during the interim analysis. An independent Data Monitoring Committee (DMC) will perform the futility analysis. The DMC will make recommendation to Amgen regarding the continuation of the study. The DMC will be supported by an independent biostatistics group which is responsible for preparing reports. Details regarding**

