## 12.3 Appendix 3. Study Governance Considerations

### Data Monitoring Committee

An Independent Biostatistics Group (IBG) will perform periodic safety analyses for review by an independent Data Monitoring Committee (DMC), which will include at least 2 clinicians and at least 1 biostatistician who are external to Amgen. The IBG and DMC will have access to subjects' individual treatment assignments. To minimize the potential introduction of bias to the conduct of the study, members of the DMC and Data Monitoring Group will not have any direct contact with study site personnel or subjects. The DMC will communicate major safety concerns and recommendations regarding study modification or termination based on the safety parameters to Amgen in accordance with the DMC charter. The DMC **will** also review **the interim futility analysis results** to assess if the study should stop for futility.

Records of all meetings will be maintained by the DMC for the duration of the study. Records of all meetings will be transferred and stored in the trial master folder at the conclusion of the study. Further details are provided in the DMC charter.

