7.1 Interim Analysis and Early Stopping Guidelines

One interim futility analysis will be performed at approximately 81 subjects completing three cycles of chemotherapy. The primary endpoint, which is the proportion of subjects with no thrombocytopenia-induced chemotherapy dose modification in the second and third cycles of the planned on-study chemotherapy regimen, will be analyzed at the interim analysis. Dose

modification assessments will be based on the central review by the independent adjudication committee. The futility boundary for the primary endpoint is p-value of 0.438, which corresponds to an OR of 1.086. The study may be stopped for futility if the non-binding futility boundary is crossed.

Due to slow enrollment, there will be no enrollment pause during the interim analysis. An independent Data Monitoring Committee (DMC) will perform the futility analysis. The DMC will make recommendation to Amgen regarding the continuation of the study. The DMC will be supported by an independent biostatistics group which is responsible for preparing reports. Details regarding the responsibilities of the DMC and the independent biostatistics group will be described in the DMC Charter.

Records of all meetings will be submitted to the TMF per the DMC Charter and in accordance with SOP-427356. Further details are provided in the DMC charter.

The Data Access Plan (DAP) will be invoked if the DMC recommends early stopping for efficacy. The DAP Team will make the decisions on further conduct of the study and will decide on any further action which may include, for example, external communication to a regulatory agency, study team, unblinding, and/or changes to study conduct. Further details are provided in the DAP.

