9.1 General Considerations

Continuous variables will be summarized descriptively by the n, mean, standard deviation, median, Q1 (25th percentile), Q3 (75th percentile), minimum, and maximum. The confidence interval and standard error for the mean will also be summarized for efficacy variables that are continuous. Categorical variables will be summarized descriptively by the number and percentage in each category. Missing values will be shown as a separate category. The confidence interval will also be summarized for dichotomous efficacy variables.

Time to event variables will be summarized with hazard ratios, Kaplan-Meier curves, Kaplan-Meier quartiles, the number of subjects at risk, the number of subjects censored, and the number of subjects with events.

Where confidence intervals are provided, these will be 2-sided at the 95% level, unless otherwise specified.

The primary efficacy endpoint will be compared between the romiplostim and placebo groups at the significance level of 0.05 using a 2-sided test. If statistical significance is achieved for the primary endpoint in favor of romiplostim, **the following secondary efficacy endpoints will be tested using a fixed sequence hierarchical testing procedure to control the family-wise Type I error rate below 2-sided 0.05 level. The family of hypotheses is ordered as follows:**

- the depth of platelet count nadir from the start of the first on-study chemotherapy cycle through the end of the treatment period
- the time to first platelet response, defined by platelet count $\geq 100 \times 10^9/L$, in the absence of platelet transfusions during the preceding 7 days.
- the duration-adjusted event rate of \geq grade 2 bleeding events as assessed per CTCAE version 5.0 grading scale
- overall survival
- platelet transfusion(s) during the treatment period
- achieving platelet count $\geq 100 \times 10^9/L$ at any time after study day 1 to week 4 (ie, 7 days after the planned third dose of investigational product) in the absence of platelet transfusions during the preceding 7 days

Starting with the hypothesis of platelet count nadir, if any null hypothesis in the sequence is rejected at a 2-sided significance level of 0.05, then the subsequent hypothesis will be tested; if any null hypothesis is accepted, then the subsequent hypotheses will not be tested.

Summary statistics without formal testing will be provided for other endpoints.

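### The 84% power attached to the 81-subject interim matches the full 162-subject analysis (about 54% to 56% at 81), and SAP 7.1 keeps an efficacy-stop action in a futility-only interim

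*SAP*

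**What the plan says.** **Power and futility probability.** SAP 3.2 places the single interim at about 81 subjects, half of the planned 162. For a control arm with 35% of subjects unmodified in one cycle, it then says that "the power is estimated to be 84% at the interim analysis and the probability of stopping for futility is 2" percent. Protocol 10.1 and the synopsis carry the same sentence. None of the three restates the romiplostim rate or the cycle correlation for this scenario. The base case just before it has one-cycle rates "assumed to be 30% and 60% respectively, with a strong cycle correlation of 0.7", with 93% power at 162 subjects.

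**Interim rule.** Protocol 10.3.1.1 says "One interim futility analysis will be performed at approximately 81 subjects completing three cycles of chemotherapy". SAP 7.1 adds: "The futility boundary for the primary endpoint is p-value of 0.438, which corresponds to an OR of 1.086", and "The study may be stopped for futility if the non-binding futility boundary is crossed". Protocol Appendix 3 has the data monitoring committee review the interim results "to assess if the study should stop for futility". No efficacy boundary or interim alpha is given, and SAP 9.1 tests the primary endpoint "at the significance level of 0.05 using a 2-sided test".

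**Efficacy action.** SAP 7.1 nevertheless ends with: "The Data Access Plan (DAP) will be invoked if the DMC recommends early stopping for efficacy".

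**Synopsis label.** The synopsis presents 30% and 60% as primary-endpoint rates. Protocol 10.1 and SAP 3.2 use them as one-cycle rates.

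**The concern.** An 84% power from 81 subjects is hard to reconcile with 93% from 162 when the 84% scenario assumes a smaller treatment difference. If the 84% belongs to the full sample, the sentence misstates what the interim can show. It also obscures a useful sensitivity result: the cost in final power of a 35% control rate.

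The efficacy sentence in SAP 7.1 is a separate problem. It names a procedure for a recommendation that the plan gives the committee no rule to make. Keeping the full two-sided 0.05 at the end is sound only while the interim cannot lead to an efficacy claim.

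**Working it through.** **Inputs.** From SAP 3.2 and Protocol 10.1: 2:1 allocation, 108/54 at N = 162 (hence 54/27 at N = 81), two-sided 0.05, CMH test, and endpoint rate p² + ρp(1 − p) for one-cycle rate p and correlation ρ. From SAP 7.1: boundary p = 0.438, OR 1.086. Assumed: romiplostim 60% and ρ = 0.7 carry over to the 35% scenario.

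**Endpoint rates at ρ = 0.7**
- p = 0.30: 0.09 + 0.7 × 0.21 = 0.237
- p = 0.35: 0.1225 + 0.7 × 0.2275 = 0.282
- p = 0.60: 0.36 + 0.7 × 0.24 = 0.528

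**Method (log odds ratio).** Power = Φ(ln OR / SE − 1.96), with SE² = 1/[n_c p_c(1 − p_c)] + 1/[n_t p_t(1 − p_t)].

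**Step 1: reproduce the 93%.** For 0.528 vs 0.237, OR = 3.60 and ln OR = 1.281. At N = 162, SE = 0.374, so power = Φ(3.430 − 1.96) = 92.9%. This matches the plan.

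**Step 2: the 35% scenario.** For 0.528 vs 0.282, OR = 2.85 and ln OR = 1.048.
- N = 162: SE = 0.359, power = Φ(2.921 − 1.96) = 83.2%
- N = 81: SE = 0.507, power = Φ(2.066 − 1.96) = 54.2%

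| Method (two-sided 0.05) | N = 162 | N = 81 |
|---|---|---|
| Log odds ratio | 83.2% | 54.2% |
| Difference, pooled variance | 85.9% | 56.0% |
| Difference, unpooled variance | 88.6% | 60.9% |
| Pooled, continuity-corrected | 81.6% | 46.0% |
| Stratified CMH, simulated (assumed six-stratum mixes) | 84.2% to 84.9% | 53.8% to 54.3% |
| Same, continuity-corrected | 80.2% to 80.3% | 43.5% to 44.0% |

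Net of a futility stop at the interim, final power is 82.7% (log odds ratio) to 83.9% (pooled-variance drift). No variant reaches 84% at 81 subjects.

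**Step 3: how to read the boundary.** One-sided, p = 0.438 gives z = 0.156. With the base-case SE at N = 81 (0.528), the odds ratio at the boundary is exp(0.156 × 0.528) = 1.086, the printed value. Two-sided, z = 0.776 gives exp(0.776 × 0.528) = 1.51. The boundary is therefore one-sided, at 81 subjects.

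**Step 4: the 2%.** Futility probability = Φ(0.156 − ln OR / SE).
- N = 81: Φ(0.156 − 2.066) = 2.8%; pooled variance 1.9%; CMH simulation 2.5% to 2.6%
- N = 162: Φ(0.156 − 2.921) = 0.28%; pooled variance 0.14%

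The 2% belongs to the 81-subject look.

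**Step 5: sensitivity to the assumed inputs.** With 60% kept and ρ anywhere from 0 to 1, log-OR power stays at 83.2% to 85.6% for N = 162 and 54.2% to 57.1% for N = 81, so the correlation hardly matters. A 70% romiplostim rate gives 83.2% (log odds ratio) to 87.4% (pooled) at N = 81, but the futility probability is then only 0.28% to 0.10%.

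**Synopsis label.** Using 30%/60% directly as endpoint rates at N = 162 gives 94.0% (log odds ratio) or 96.0% (pooled), against 92.9% and 95.7% for 23.7%/52.8%. The difference is about one point or less.

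**The case against.** **The number is right and only its label is wrong.** The sponsor very probably meant final power re-estimated for the design with an interim, and 83% to 84% net of the futility stop fits that. Nothing operational depends on the 84%; the decision rule is the non-binding boundary. This stands, and it is why the remedy is wording only.

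**The harm depends on a literal reading.** A futility look has no success criterion, so power at 81 subjects is not a defined quantity in this plan. Both 93% and 84% are also printed in the same section, so the drop is mislabelled, not concealed. That is fair. But three places attach the figure to the interim, and readers can only take the text as it stands.

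**The gap is less precise than 28 to 30 points.** Across all test variants, power at 81 subjects runs from about 43% to 61%. The 54% to 56% figure comes from the main methods. The conclusion is the same throughout the range.

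**Another set of inputs might fit.** With 0.438 read as two-sided and a 70% romiplostim rate, the log-OR method at 81 subjects gives 83.2% power and a 1.6% futility probability, close to the printed pair. This is the strongest counter-argument. It fails because the printed OR of 1.086 reproduces only on the one-sided reading (1.51 on the two-sided). One-sided, the 70% rate gives a futility probability of at most 0.3%.

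**The Data Access Plan and committee charter are not available here.** They could contain an efficacy rule, so the remedy for that sentence is to delete or reconcile it.

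**Conclusion.** The concern holds.

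- **Power label.** On the plan's formula, with 60% and 0.7 carried over, 84% matches the 162-subject analysis (83% to 86%; 80% to 82% with continuity correction). It does not match the 81-subject interim. The paired 2% is an interim figure, so one sentence mixes two analyses. That 84% is final-analysis power is inferred from this match; the documents do not say so.
- **Efficacy trigger.** The sentence in SAP 7.1 conflicts with the futility-only design described in the same section, Protocol 10.3.1.1 and Appendix 3. Type I error is unaffected as long as no efficacy stop is made.
- **Synopsis label.** Wrong but minor.

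These points should be corrected. None of them undermines the sample size or the primary test.

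**What to change.** 1. In the synopsis, Protocol 10.1 and SAP 3.2, once the sponsor confirms the inputs, replace the sentence with wording such as: *with one-cycle rates of 35% (control) and 60% (romiplostim) and cycle correlation 0.7, final-analysis power (N = 162) is about 84%; the chance of a futility stop at the interim is about 2%.*
2. In SAP 7.1, delete the efficacy trigger, or reconcile it with the futility-only design, the Data Access Plan and the committee charter. State that the interim will not be used to claim efficacy.
3. In the synopsis, label 30%/60% as one-cycle rates, or give 23.7%/52.8% as the endpoint rates.

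The cost is protocol and SAP wording only.
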